Trail title: Sintilimab (PD-1 inhibitor) Combined with Ramucirumab (a VEGFR-2 antagonist) and Chemotherapy as First-line Treatment in Patients with Advanced Gastric Cancer with Liver Metastasis (RAMSINT): A Phase II, Single-center, Prospective Clinical Study

Study protocol and statistical analysis plan

Sponsor:

Department of Oncology,
The First Affiliated Hospital of Nanjing Medical University,
[name],
[name],
Jiangsu Province,
China

Protocol version number:

RAMSINT v1.0, dated 11, June 2024

CONFIDENTIALITY STATEMENT

The information is provided to you in confidence to enable you to perform the work. Do not give this document or any copy of it or reveal any proprietary information contained in it to any third party or person without the prior permission of an authorization.

Protocol synopsis

Study Title	Phase II clinical study of Sintilimab (PD-1 Inhibitor) Combined with Ramucirumab (a VEGFR-2 antagonist) and chemotherapy as first-line treatment in patients with advanced gastric cancer with liver metastasis
Study purpose	To observe the efficacy and safety of Sintilimab combined with Ramucirumab and chemotherapy as a first-line treatment for patients with advanced gastric cancer with liver metastasis, and to explore the clinical indicators related to the efficacy, so as to guide the subsequent individualized treatment
Study design	A prospective, single-arm, single-center, phase II clinical trial
Study patients	Patients with advanced gastric cancer liver metastasis diagnosed and receiving first-line treatment at our center from August 2024 to July 2025
Total number of cases	39 patients with gastric cancer liver metastasis
Criteria for patients enrolled	
Inclusion criteria:
 
 1. Voluntary participation in the clinical study; full understanding and informed consent to this study by signing the Informed Consent Form (ICF); willingness to follow and ability to complete all trial procedures. 2. Gender is not restricted, and participants must be at least 18 years old when signing the ICF. 3. Patients with histologically or cytologically confirmed, unresectable, or who refuse surgical resection of locally advanced, recurrent, or metastatic gastric and gastroesophageal junction (GEJ) adenocarcinoma (including signet-ring cell carcinoma, mucinous adenocarcinoma, hepatoid adenocarcinoma, etc.). (Note: For patients who relapse after neoadjuvant/adjuvant therapy, the time from the end of neoadjuvant/adjuvant therapy to disease relapse

	
must be more than 6 months.)
 
4. Patients, except those with recurrent disease after neoadjuvant/adjuvant therapy, must not have previously received systemic treatment.
 
5. Participants must be histologically confirmed as having HER2-negative gastric cancer, GEJ cancer, or esophageal adenocarcinoma.
 
6. There must be at least one measurable lesion in the liver assessed by computed tomography (CT) scan or magnetic resonance imaging (MRI) according to the Response Evaluation Criteria in Solid Tumors (RECIST 1.1) that can undergo repeat radiological evaluation; the radiological tumor assessment should be performed within 28 days prior to randomization.
 
7. The Eastern Cooperative Oncology Group (ECOG) Performance Status (PS) score of 0-2 within 7 days prior to the first dose of medication.
 
8. Expected survival greater than or equal to 3 months.
 
9. Hepatitis B surface antigen (HBsAg) negative and hepatitis B core antibody (HBcAb) negative. If HBsAg positive or HBcAb positive, hepatitis B virus deoxyribonucleic acid (HBV-DNA) must be less than 1000 copies/mL or less than 200 IU/mL or less than the upper limit of normal (ULN) at the research center for enrollment to occur.
 
10. HCV antibody negative.
 
11. Main organ functions must be normal, meeting the following criteria (no blood transfusions, albumin, recombinant human thrombopoietin, or colony-stimulating factor (CSF) treatments within 14 days prior to the first dose):
 
a. Hematological System
 
 
 White Blood Cells (WBC)	Normal range	
 
 Neutrophils (NE)	Normal range	
 
	White Blood Cells (WBC)	Normal range	Neutrophils (NE)	Normal range
White Blood Cells (WBC)	Normal range				
Neutrophils (NE)	Normal range				

	Platelets (PLT)	$\geq 100 \times 10^9/L$
	Hemoglobin (Hb)	$\geq 90 \text{ g/L}$
b. Liver Function		
	Total Bilirubin (TBIL)	$\leq 1.5 \times \text{ULN}$
	Alanine Aminotransferase (ALT)	$\leq 5.0 \times \text{ULN}$
	Aspartate Aminotransferase (AST)	$\leq 5.0 \times \text{ULN}$
	Albumin	$\geq 30 \text{ g/L}$
c. Renal Function		
	Creatinine (Cr)	Normal range
d. Coagulation Function		
	Activated Partial Thromboplastin Time (APTT)	$\leq 1.5 \times \text{ULN}$
	Prothrombin Time (PT)	$\leq 1.5 \times \text{ULN}$
	International Normalized Ratio (INR)	$\leq 1.5 \times \text{ULN}$
12. Availability of representative tumor tissue specimens, blood samples, and fecal samples for exploratory research.		
Exclusion criteria:		
1. History of other active malignancies within the past 5 years or currently having other active malignancies. Treated localized tumors, such as basal cell carcinoma of the skin, squamous cell carcinoma of the skin, superficial bladder cancer, prostate carcinoma in situ, cervical carcinoma in situ, and breast carcinoma in situ, are eligible for inclusion.		
2. Underwent surgery within 4 weeks prior to the start of the study treatment.		
3. Presence of central nervous system diseases or symptoms of central nervous system metastasis.		
4. Patients preparing for or with a history of organ or bone marrow transplantation.		

	
5. History or evidence of thrombosis or bleeding disorders within 6 months prior to the first study treatment.6. Diagnosis of active pulmonary tuberculosis.7. History or presence of interstitial pneumonia, pneumoconiosis, radiation pneumonia, drug-induced pneumonia, or other conditions that may interfere with the detection and management of suspected drug-related pulmonary toxicity.8. Uncontrolled hypertension (SBP \geq 150 and/or DBP \geq 100) or history of hypertensive crisis or cardiovascular diseases (\geq II degree or worse congestive heart failure, myocardial ischemia, unstable angina, stroke, or transient ischemic attack).9. Patients with high-risk factors for gastrointestinal perforation (history of gastrointestinal fistula, perforation, abdominal abscess, partial or complete intestinal obstruction, or requiring total parenteral nutrition).10. Patients with moderate to severe proteinuria.11. Patients with non-healing wounds, ulcers, or fractures.12. Presence of known active or suspected autoimmune diseases, except those who are in a stable condition at the time of enrollment (not requiring systemic immunosuppressive treatment).13. Known history of severe allergy to any monoclonal antibodies or excipients.14. Known history of substance abuse or drug addiction; patients who have stopped alcohol consumption can be included.15. Patients with conditions that may increase the risk associated with the study drugs, or other severe, acute, and chronic diseases, as judged by the investigator, are deemed unsuitable for participation in the clinical study.16. Previous use of PD-1 inhibitors, LAG-3 inhibitors, CTLA-4
--	---

	
inhibitors, or any other antibodies or drug treatments targeting T-cell co-stimulation or immune checkpoint pathways, including previous receipt of anti-tumor vaccines or other immunostimulatory anti-tumor therapies.
 
17. Previous exposure to VEGF (vascular endothelial growth factor) or VEGFR inhibitors or any anti-angiogenesis medications.

Study design	
After enrollment, the participants will receive a combined treatment regimen of Sintilimab, Ramucirumab and chemotherapy. The chemotherapy regimen will include one of the following two combination therapies: SOX regimen (oxaliplatin and S-1) or XELOX regimen (oxaliplatin and capecitabine). A maximum of 6 cycles of combination treatment will be administered, with each cycle lasting 21 days. After completing the 6 cycles of combined treatment regimen, the participants will receive Sintilimab and oral chemotherapy agents (Capecitabine or S-1) with or without Ramucirumab until disease progression. In case of disease progression or intolerable toxic reactions occur during treatment, the investigator will determine the subsequent treatment options.
 
The specific dosages and methods for the medications mentioned above are as follows:
 
Immunotherapy:
 
Sintilimab: 200mg fixed dose, intravenous infusion on Day 1, repeated every 21 days.
 
Targeted Therapy:
 
Ramucirumab: 10mg/kg intravenous infusion on Day 1, repeated every 21 days.
 
Chemotherapy: Two combination regimens include:
 
SOX regimen: Oxaliplatin 130mg/m² intravenous infusion on Day 1 and S-1 40mg/m² orally twice daily on Days 1-14, repeated every 21

days.

XELOX regimen: Oxaliplatin 130mg/m² intravenous infusion on Day 1 and Capecitabine 1000mg/m² orally twice daily on Days 1-14, repeated every 21 days.

Imaging assessments (CT/MRI) are required before the first treatment and after every two cycles of treatment. Gastric tissue specimens will be collected from patients prior to the first treatment (paraffin sections) (5-20 slices of surgical tissue (each tissue more than 1cm²), or 20-25 slices of puncture tissue). Blood samples and stool samples will be collected before the first treatment, after every two cycles, or at the time of disease progression to analyze the corresponding samples collected at baseline, when the best overall efficacy appears, or upon disease progression (Blood samples: approximately 5ml per instance; fecal samples: middle segment stool, the size of a soybean (approximately 50 mg), collected in three tubes). The expression levels of 92 proteins in blood samples will be dynamically monitored using the Olink-96 Immune-Oncology panel. Intratumoral microbiota in baseline tumor tissue samples will be detected using 5R 16S rRNA sequencing, and gut microbiota in stool samples will be detected using 16S rRNA sequencing.

Study Assessment	
Primary Endpoint:
 
Objective Response Rate (ORR): The proportion of participants whose tumor volume decreases to a predefined value and can maintain the minimum duration requirements, which is the sum of the rates of Complete Response (CR) and Partial Response (PR).
 
Secondary Endpoints:
 
 Disease Control Rate (DCR): The proportion of participants who achieve either a response (PR + CR) or Stable Disease (SD) after treatment and can maintain the minimum duration requirements. Progression-Free Survival (PFS): The time from the start of treatment to disease progression or death (from any cause). Overall Survival (OS): The time from enrollment to death due to any cause. Incidence of adverse events and serious adverse events (AEs): Categorized according to the Common Terminology Criteria for Adverse Events version 5.0 (CTCAE 5.0). Descriptive statistical analysis is primarily used to list and describe the AEs that occurred during this trial. 
Exploratory Endpoints:
 
To identify potential predictive indicators of efficacy (including the distribution of intratumoral microorganisms in tumor tissue, protein expression levels in serum samples, and the distribution of gut microbiota in fecal samples, etc.).

Statistical analysis plan	
Intent-to-Treat Population (ITT): Defined as all subjects who entered the trial. The ITT population will serve as the primary population for efficacy analysis in this study.
 
Per-Protocol Population (PPS): The per-protocol population is a subset of the ITT population, consisting of participants who were randomly assigned, received at least one treatment, and underwent

tumor assessment without significant protocol deviations that would affect the primary efficacy evaluation. Analyses based on PPS will serve as supportive analyses to complement the ITT-based analyses.

Safety Analysis: Safety analysis will primarily involve descriptive statistics, listing adverse events (AE) that occurred during the trial. Laboratory test results will describe abnormalities that were normal before the trial but became abnormal after treatment, along with their relationship to the trial drug when abnormal changes occurred.

Efficacy Analysis: The Objective Response Rate (ORR) will be calculated as the proportion of patients in the ITT population who achieved the best overall response of complete response (CR) or partial response (PR). The Disease Control Rate (DCR) will be calculated as the proportion of patients in the ITT population who achieved the best overall response of CR, PR, or stable disease (SD). For efficacy endpoints such as overall survival (OS) and progression-free survival (PFS), the Kaplan-Meier method will be used to estimate the median times and list the median events along with their two-sided 95% confidence intervals.

Patient data and outcome parameters will be inputted into GraphPad Prism (version 9.1.2) and analyzed using the non-parametric Mann-Whitney U test (for continuous variables) to compare differences between two groups. For comparisons among more than two patient groups, the non-parametric Kruskal-Wallis test will be applied, followed by Dunn's post-hoc test with Bonferroni correction. Fisher's exact test will be used for intergroup comparisons of categorical variables.

The serum protein abundance data from patients receiving Sintilimab + Ramucirumab + chemotherapy will be analyzed using the Cox proportional hazards model and Benjamini-Hochberg

	
multiple hypothesis correction ("R," version 4.2.1). A sample will be identified as an outlier using PCA plots and median vs. interquartile range (IQR) plots. This sample will be excluded from the phase one analysis. Samples with QC warning status will also be excluded from both analyses on a per-panel basis. The results will then be adjusted for multiple testing using the Benjamini-Hochberg method. Hazard ratio (HR) will be based on 1 NPX difference. The association between baseline NPX (v1) and ΔNPX (Δv2/v3-v1) plasma protein levels and PFS will be assessed by plotting Kaplan-Meier curves and calculating log-rank p-values. Patients receiving Sintilimab + Ramucirumab + chemotherapy will be evaluated by dividing them into low or high expression "risk groups" based on the median expression values of each parameter as a threshold. For all statistical analyses, a p-value of less than 0.05 will be considered statistically significant.

Research progress	August 2024 - July 2026

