4 STUDY POPULATION

4.1 Inclusion criteria

1. Voluntary participation in the clinical study; full understanding and informed consent to this study by signing the Informed Consent Form (ICF); willingness to follow and ability to complete all trial procedures.
2. Gender is not restricted, and participants must be at least 18 years old when signing the ICF.
3. Patients with histologically or cytologically confirmed, unresectable, or who refuse surgical resection of locally advanced, recurrent, or metastatic gastric and gastroesophageal junction (GEJ) adenocarcinoma (including signet-ring cell carcinoma, mucinous adenocarcinoma, hepatoid adenocarcinoma, etc.). (Note: For patients who relapse after neoadjuvant/adjuvant therapy, the time from the end of neoadjuvant/adjuvant therapy to disease relapse must be more than 6 months.)
4. Patients, except those with recurrent disease after neoadjuvant/adjuvant therapy, must not have previously received systemic treatment.
5. Participants must be histologically confirmed as having HER2-negative gastric cancer, GEJ cancer, or esophageal adenocarcinoma.
6. There must be at least one measurable lesion in the liver assessed by computed tomography (CT) scan or magnetic resonance imaging (MRI) according to the Response Evaluation Criteria in Solid Tumors (RECIST 1.1) that can undergo repeat radiological evaluation; the radiological tumor assessment should be performed within 28 days prior to randomization.
7. An Eastern Cooperative Oncology Group (ECOG) Performance Status (PS) score of 0-2 within 7 days prior to the first dose of medication.
8. Expected survival of greater than or equal to 3 months.
9. Hepatitis B surface antigen (HBsAg) negative and hepatitis B core antibody (HBcAb) negative. If HBsAg positive or HBcAb positive, hepatitis B virus deoxyribonucleic acid (HBV-DNA) must be less than 1000 copies/mL or less than 200 IU/mL or less than the

upper limit of normal (ULN) at the research center for enrollment to occur.

10. HCV antibody negative.

11. Main organ functions must be normal, meeting the following criteria (no blood transfusions, albumin, recombinant human thrombopoietin, or colony-stimulating factor (CSF) treatments within 14 days prior to the first dose):

a. Hematological System

White Blood Cells (WBC)	Normal range
Neutrophils (NE)	Normal range
Platelets (PLT)	$\geq 100 \times 10^9/L$
Hemoglobin (Hb)	$\geq 90 \text{ g/L}$

b. Liver Function

Total Bilirubin (TBIL)	$\leq 1.5 \times \text{ULN}$

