Alanine Aminotransferase (ALT)	$\leq 5.0 \times \text{ULN}$
Aspartate Aminotransferase (AST)	$\leq 5.0 \times \text{ULN}$
Albumin	$\geq 30 \text{ g/L}$

c. Renal Function

Creatinine (Cr)	Normal range
-----------------	--------------

d. Coagulation Function

Activated Partial Thromboplastin Time (APTT)	$\leq 1.5 \times \text{ULN}$
Prothrombin Time (PT)	$\leq 1.5 \times \text{ULN}$
International Normalized Ratio (INR)	$\leq 1.5 \times \text{ULN}$

12. Availability of representative tumor tissue specimens, blood samples, and fecal samples for exploratory research.

Exclusion criteria:

1. History of other active malignancies within the past 5 years or currently having other active malignancies. Treated localized tumors, such as basal cell carcinoma of the skin, squamous cell carcinoma of the skin, superficial bladder cancer, prostate carcinoma in situ, cervical carcinoma in situ, and breast carcinoma in situ, are eligible for inclusion.
2. Underwent surgery within 4 weeks prior to the start of the study treatment.

3. Presence of central nervous system diseases or symptoms of central nervous system metastasis.
4. Patients preparing for or with a history of organ or bone marrow transplantation.
5. History or evidence of thrombosis or bleeding disorders within 6 months prior to the first study treatment.
6. Diagnosis of active pulmonary tuberculosis.
7. History or presence of interstitial pneumonia, pneumoconiosis, radiation pneumonia, drug-induced pneumonia, or other conditions that may interfere with the detection and management of suspected drug-related pulmonary toxicity.
8. Uncontrolled hypertension (SBP \geq 150 and/or DBP \geq 100) or history of hypertensive crisis or cardiovascular diseases (\geq II degree or worse congestive heart failure, myocardial ischemia, unstable angina, stroke, or transient ischemic attack).
9. Patients with high-risk factors for gastrointestinal perforation (history of gastrointestinal fistula, perforation, abdominal abscess, partial or complete intestinal obstruction, or requiring total parenteral nutrition).
10. Patients with moderate to severe proteinuria.
11. Patients with non-healing wounds, ulcers, or fractures.
12. Presence of known active or suspected autoimmune diseases, except those who are in a stable condition at the time of enrollment (not requiring systemic immunosuppressive treatment).
13. Known history of severe allergy to any monoclonal antibodies or excipients.

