6. OBSERVATIONAL ITEMS AND TESTING POINTS

Screening Period: Once patients are enrolled, blood tests (including complete blood count, coagulation function, tumor markers, myocardial markers, thyroid function, and microprotein expression levels) will be conducted one week before the start of the first treatment cycle, along with the collection of fecal samples, chest and abdominal imaging (plain scan or enhanced scan), and cardiac function evaluation (two-dimensional echocardiogram). Patients' age, gender, and other basic clinical data will be collected and organized. Gastric mucosal tissue specimens will be collected for intratumoral microbiome detection before the first treatment.

After Every 2 Treatment Cycles: After every 2 cycles of treatment with Sintilimab, Ramucirumab and chemotherapy, peripheral blood and fecal samples will be collected, and peripheral blood microprotein expression levels and gut microbiome analysis will be conducted during imaging assessments when the best overall efficacy is observed.

Disease Progression: If patients experience symptom deterioration or new symptoms, peripheral blood microprotein expression levels and fecal gut microbiome analyses will be performed within one week after confirming symptom deterioration or the emergence of new symptoms.

Follow-Up Period: During the treatment period, if the patient's disease does not progress, follow-ups are required every 3 months following the completion of 6 cycles of treatment, including: (1) routine follow-up assessments: clinical history, physical examination, routine hematological tests (complete blood count and chemical analysis, tumor markers CEA and CA199), Helicobacter pylori testing, nutritional evaluation (vitamin B12, iron), and enhanced CT scans of the chest, abdomen, and pelvis; (2) If patients experience symptom deterioration or new symptoms emerge, blood and fecal sample collections must be completed within one week, along with peripheral blood protein detection and gut microbiome analyses. Upon the patient's death, overall survival (OS) will be recorded, marking the clinical trial observation endpoint.

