10. DATA SAFETY MONITORING

The clinical study will establish a corresponding data safety monitoring plan based on the level of risk involved. All adverse events will be documented in detail, appropriately handled, and tracked until resolved or the patient's condition is stabilized. Serious adverse events and unexpected events will be promptly reported to the ethics committee, regulatory authorities, sponsors, and drug supervision departments as required. The principal investigator will conduct regular cumulative reviews of all adverse events and will convene investigator meetings to assess the risks and benefits of the study when necessary. Studies with risks greater than minimum will arrange for independent data monitors to oversee the study data, and high-risk studies will establish an independent Data Safety Monitoring Board (DSMB) to review accumulated safety and efficacy data and make recommendations on whether the study should continue.

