11. STATISTICAL PROCESSING

Intention-to-Treat (ITT) Population: Defined as all participants who entered the trial; the ITT population will serve as the primary analysis group for this study's efficacy evaluation.

Per-Protocol Set (PPS): The PPS is a subset of the ITT population, consisting of participants who were randomly assigned and underwent at least one treatment with tumor assessment and who had no significant protocol deviations that could materially affect primary efficacy evaluations. Analysis based on the PPS will serve as supportive analysis to complement the ITT-based analysis.

Safety Set (SS): Defined as all participants who received at least one dose of the investigational drug. The safety analysis population will be the primary analysis group for safety indicators and will be based on the treatment groups actually received.

Kaplan-Meier methods will be used to summarize Progression-Free Survival (PFS) and Overall Survival (OS); results will provide the median PFS and OS, along with 95% confidence intervals for all participants in the trial (ITT population). The Objective Response Rate (ORR) (defined as CR + PR) and Disease Control Rate (DCR)

(defined as CR + PR + SD) will be estimated with 95% credible intervals. Adverse event data for all participating patients will be summarized using descriptive statistics.

Patient data and outcome parameters will be entered into GraphPad Prism (version 9.1.2) and analyzed using the non-parametric Mann-Whitney U test (for continuous variables) to compare differences between two groups. For comparisons among more than two patient groups, the non-parametric Kruskal-Wallis test will be employed, followed by Dunn's post-hoc test with Bonferroni correction. Fisher's exact probability method will be used for between-group comparisons of categorical variables.

For all statistical analyses, a p-value of less than 0.05 will be considered statistically significant.

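### The only laboratory-summary rule covers normal-to-abnormal changes, so worsening from a raised liver or coagulation test that eligibility admits is left out of the laboratory summary

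*Combined protocol and SAP*

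**What the plan says.** The rule is in the protocol synopsis, Statistical analysis plan, Safety Analysis: "Laboratory test results will describe abnormalities that were normal before the trial but became abnormal after treatment". The same sentence adds the relationship of those changes to the trial drug. Section 11 (Statistical Processing) defines the Safety Set, "Defined as all participants who received at least one dose of the investigational drug", and says of safety data only that "Adverse event data for all participating patients will be summarized using descriptive statistics". It has no laboratory rule.

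Inclusion criterion 11 (synopsis and section 4.1) opens with "Main organ functions must be normal, meeting the following criteria" and then gives a limit for each test. ALT and AST may be up to 5 x ULN. Total bilirubin, APTT, PT and INR may be up to 1.5 x ULN. WBC, neutrophils and creatinine must lie in the normal range.

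Adverse events are classified by CTCAE 5.0 (synopsis, secondary endpoints). Section 10 says "All adverse events will be documented in detail, appropriately handled, and tracked until resolved" or the patient's condition is stable. Section 8 describes what adverse events mainly include and does not mention laboratory worsening.

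**The concern.** The reporting rule and the entry limits do not fit together. The rule takes a normal starting value as its condition, while eligibility expressly allows abnormal starting values in the liver enzymes, bilirubin and coagulation tests. Followed as written, the laboratory summary would leave out the patients who began with raised values.

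Safety is part of the study purpose, and every patient must have a measurable liver lesion. This is also a single-arm study of 39 patients. With no control group, each patient's change from baseline is the main evidence on laboratory toxicity. If a patient's ALT rose from 4 to 20 x ULN, a reader of the laboratory summary would not see it and would depend on whether someone had also entered it as an adverse event. The description of the relationship to the drug is tied to the same normal-to-abnormal changes, so it would be missing as well.

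**Working it through.** The plan gives no figure to reproduce, and no rate can be calculated. The check compares the rule with the entry limits and then looks for any other rule that would close the gap.

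**1. Entry limits set against the rule (criterion 11, section 4.1)**

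| Tests | Limit at entry | Can the value be abnormal at entry? | Does the rule cover worsening? |
|---|---|---|---|
| ALT, AST | up to 5 x ULN | Yes | Only if at or below the ULN at entry |
| Total bilirubin, APTT, PT, INR | up to 1.5 x ULN | Yes | Only if at or below the ULN at entry |
| WBC, neutrophils, creatinine | normal range | No | Covers every new abnormality |
| Haemoglobin, platelets, albumin | at least 90 g/L, 100 x 10^9/L, 30 g/L | Only if the local lower limit of normal is above the entry limit (not given) | Depends on that limit |

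Count: 2 + 4 = 6 tests may be above the ULN at entry, 3 must be normal and 3 are undetermined; 6 + 3 + 3 = 12. The 6 include three of the four tests listed under liver function (the fourth is albumin) and all three under coagulation.

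**2. What normal means before the trial**

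- *Literal reading (within the reference range).* ALT of 4 x ULN at entry is eligible but not normal. A rise to 20 x ULN is not described.
- *Alternative reading (within the entry limits), prompted by the lead-in to criterion 11.* A rise from 4 to 20 x ULN crosses the 5 x ULN limit and is described. A rise from 1.5 to 4.5 x ULN stays inside the limit and is not.

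The criterion 11 table uses the normal range as a separate, stricter limit for three tests. That separates a normal value from an eligible one and supports the literal reading. The plan states neither, and each leaves some worsening out.

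**3. Search for another rule**

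- Section 6 lists tests but not how they are summarised.
- Section 8 has no rule for laboratory shifts or grades.
- Section 10 requires adverse events to be documented and tracked, but does not say when a laboratory change is one.
- Section 11 summarises adverse events only.

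**4. Data that a fuller summary would need**

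Section 6 names for screening "blood tests (including complete blood count, coagulation function, tumor markers, myocardial markers, thyroid function, and microprotein expression levels" and some further items. Liver tests are not named, although the list is introduced as non-exhaustive and criterion 11 cannot be checked without them. Chemistry is named only at the 3-monthly follow-up after 6 cycles: "routine hematological tests (complete blood count and chemical analysis, tumor markers CEA and CA199". The source of chemistry values during the six combination cycles is therefore not written down.

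**The case against.** The best counter-argument is that the safety endpoint does not rest on this sentence. The secondary endpoint is the incidence of adverse events by CTCAE 5.0, safety analysis is primarily a listing of those events, and all of them are to be documented and summarised. A marked ALT rise from a raised baseline could well appear there. This stands in part: the worsening is not necessarily lost to all safety reporting. But whether it appears depends on someone choosing to record it, since no rule requires that.

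A second argument is that criterion 11 calls organ function within its limits normal, so that the 4 to 20 x ULN example would be captured. That reading is possible. It narrows the gap but does not close it, as the 1.5 to 4.5 x ULN case shows.

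Third, the consequence is modest. The primary endpoint, sample size and decision rules are untouched, and the omission cannot be sized. That is correct. A shorter repair, extending the sentence to values that worsened from baseline, would also close the stated gap, though without a defined threshold or denominator.

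**Conclusion.** The concern holds. As written, the only laboratory-summary rule cannot capture worsening in a test that was already abnormal at entry, and eligibility allows this for 6 of 12 tests: ALT, AST, bilirubin, APTT, PT and INR. It may also apply to haemoglobin, platelets and albumin, on the assumption that the local lower limits of normal lie above the entry limits. WBC, neutrophils and creatinine are not affected.

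The conclusion is about the scope of the laboratory summary, not about all safety reporting. It takes normal in its reference-range sense; under the entry-limit sense a smaller gap remains. How many of the 39 patients it would touch is unknown, because the share with abnormal baseline tests is not given. The change should be made, but it does not bear on the primary ORR analysis.

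**What to change.** Replace the laboratory sentence in the synopsis, and add the same text to section 11:

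> For each laboratory test, tabulate baseline CTCAE 5.0 grade against worst on-treatment grade for all Safety Set patients with a baseline and at least one on-treatment value, and report the number with any increase in grade and with a new grade 3 or higher.

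State how a grade is assigned to a value already abnormal at baseline. If a test cannot be graded in that way, tabulate it in categories of multiples of the reference limit. In section 6, state which baseline and on-treatment laboratory values feed the table.

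The table covers every baseline level, so it works under either reading of normal. It does not settle when a laboratory change is recorded as an adverse event; that is a separate gap which the sponsor may wish to close at the same time.

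The cost is one sentence in two places, the source statement in section 6 and one set of descriptive tables. No new sampling is needed if the values behind CTCAE grading are already collected. If they are not, section 6 has to say so and the table is limited to what is available. The laboratory summary may show more toxicity than the present rule would; adverse event counts do not change.
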